1.3 MRI Assessments

All images will be performed at the University of Chicago's Magnetic Resonance Imaging Research Center (MRIRC). The MRIRC is fully dedicated to MRI research and located in the Q300 suite in the Department of Radiology of the University of Chicago Medical Center. The MRIRC houses two state of the art MRI scanners and is staffed by 2 full-time MRI technologists, research nurses, and coordinators. [name] has over 20 years' experience in neurological imaging and is the Director of Neuroimaging for the MRIRC and will oversee all aspects of imaging.

The primary outcome of all MRI techniques is to determine whether there is an improvement and subsequent stabilization/repair over time of tissue damage caused by inflammatory MS disease activity. Multiple conventional and nonconventional MR imaging modalities are examined here to determine which of these are the most sensitive and reliable in detecting microstructural damage and repair over time. The results of this study will also greatly impact the design of future MS trials by providing a guide for selecting the most appropriate MRI and immune methods to assess treatment efficacy in MS.

Conventional MRI

Quantitative T1 Gd+, T2, T1 chronic, and BPF analysis:

Commonly used MRI metrics in most studies include a post-contrast T1 weighted sequence and a T2 weighted sequence. These are useful for detecting new inflammatory lesions. The contrast-enhancing lesions are transient (less than 2 months on average) and are indicative of active lesions. The T2 lesions are more permanent and are thought to develop after enhancement ceases. Measurement of lesion load in terms of number and volume, both active and inactive (T1 Gd+, T2 chronic lesions, and T1 chronic lesions) will be examined over time.

Specific Aim: determine the effects of ACTHAR in improving the characteristics of contrast enhancing lesions (T1 Gd+) observed at baseline and followed squentially over time to the development of T2 and chronic T1 signal intensities.

Quantitative nonconventional MRIs (see Supplement for protocol details):

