2.6 Outcomes

This data may lead to better understanding of the mechanism of action of ACTHAR and identifying signatures/biomarkers in ACTHAR-treated MS. In addition, MRI, CD8+CD28- cell numbers, serum proteins, and RNA may be biomarkers for efficacy.

Part III. Patient criteria and publications

3.1a Inclusion Criteria

This study will be restricted to adult patients (>18 years) undergoing a clinical relapse who also must have a contrast-enhancing CNS lesion, either clinically or non-clinically relevant. Sample size under consideration is 18 patients. The population on which analyses will be conducted consists of all patients who have received at least 1 dose of study medication and for whom at least two time-points (baseline and at least one additional time-point) for MRI data are available (Intent-to-treat analysis).

3.1b Exclusion Criteria

1-Patients will be excluded if they only have a clinical relapse which is not associated with MRI findings of a new or enlarging MS lesion.

2-Patient will be excluded if they cannot give written consent

3-Patients will be excluded if they have an active infection

4-Patients will be excluded if they already received steroids (IV or oral) within last 30 days of receiving ACTHAR

5-Pregnant or lactating patients will be excluded from this study.

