3.4 Statistical Analysis

All data collected will be documented using summary tables, figures, and patient data listings. For longitudinal data, mixed effects regression model will be used to summarize patterns over the one-year period. All hypothesis testing will be at the 0.05 level of significance. Correlation analyses between specific measures will be accomplished using Pearson's correlation co-efficient.

All summary statistics will be displayed as a function of study visit or assessment time. Summary statistics for continuous variables will include n, mean, standard deviation, minimum, median, and maximum. For categorical variables, frequencies and percentages will be presented. Graphical displays will be provided as appropriate.

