3.11 Publication

The results of this study may be published or presented at scientific meetings. If this is foreseen, the Investigator agrees to submit all manuscripts or abstracts to Mallinckrodt prior to submission. This allows the Sponsor to protect proprietary information and to

provide comments based on information from other studies that may not yet be available to the Investigator.

Supplement: MRI Protocols

Quantitative T1/T2: We have developed a unique approach to converting standard anatomic images to quantitative values through the use of modeling of signal intensities and physics equations that define signal intensities from specific pulse sequences. We are able to standardize the T1 (in milliseconds), and then standardize the standard anatomic images that are normally used for diagnosis. In other words, we do not compromise scan time, image resolution, or patient throughput.

Standard anatomic MRI parameters include T1-weighted 3D (repetition time/echo time (TR/TE): 9.5 ms/2.3 ms, resolution: 0.63 × 0.63 × 1.2mm³) and PD/T2 (TR/TE: 2500ms/10.7ms, resolution: 0.63×0.63×1.2mm³), and will eaqui5ee before and 15 minutes post contrast. Image will be converted to T1 by calculating an MRI response function, by constraining unknowns using internal reference T1/T2 values (Normal Appearing White matter, Gray matter CSF).

Quantitative Perfusion: We have developed an MRI pulse sequence that calibrates dynamic susceptibility images to provide images of tissue perfusion in ml/100gg/min. Our pulse sequence is patented and Image parameters (FOV/matrix = 220 mm/128, 3.0 mm. 15 thick 2D slices TR/TE=1200 ms/50 ms. Fifty measurements (including calibration data) will be acquired in 3 minutes. Test-retest reliability of cerebral perfusion has been measured to be better than 14%.

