Quantification of Tissue Permeability (Ktrans): A saturation recovery gradient recalled sequence will be used both for dynamic imaging of contrast agent leakage. Each slice will be acquired after application of a nonselective saturation prepulse with a saturation time delay (*TD*). The following acquisition parameters will be used: flip angle of 30°, TR/TE =3.82 ms/1.9 ms, centric phase ordering, scan matrix size 96 × 61 (interpolated to 256 × 256), SENSE factor 2, field of view 240 × 182 mm², and four slices of 8-mm thickness, resulting in a spatial resolution of 2.5 × 3.1 × 8 mm³. The *T*₁ measurement was performed by varying the *TD* value (120 ms, 150 ms, 300 ms, 600 ms, 1 sec, 2 sec, 4 sec, 8 sec, 9 sec, 10 sec). Perfusion CBF can estimated by model-free deconvolution both for ROIs and CBF maps, blood volume *Vb* and the BBB permeability *Ktrans* will estimated both by Patlak's method and the two-compartment model.

Oxygen Extraction Fraction: As an exploratory study, we will track changes in tissues oxygenation using a novel single shot image acquisition based on a rosette k-space sampling trajectory ³⁰. A Stack of 2D slices (3 mm thick, FOV 220/matrix 65) will be acquired after a single rf pulse. A maximum-likelihood recursion will yield image for R2*(ms), Mo and local frequency shift in tissue. dw(Hz). Frequency shifts can be converted directly to Oxygen Extraction Fraction through the simple algebraic expression:

 $\delta \omega = \gamma \times \frac{4}{3} \times \pi \times \Delta \chi_0 \times \mathsf{Hct} \times \mathsf{OEF} \times B_0$

Multi-component driven equilibrium single pulse obervation of T1/T2 (mcDESPOT): This is a fairly new technique to assess the water content of myelin. In an active MS lesion, the overall water content of the lesion increases but the water associated with myelin decreases. The water pool associated with myelin has a very short T2 relaxation time compared to the other pool of intra- and extra-cellular water. Spoiled gradient echo (SPGR) and balanced steady-state free precession (bSSFP) scans are collected over a range of flip angles (FA) at constant repetition times to allow resolution of the two-pools of water, as has been previously reported ^{12,13}. The fast relaxing pool of water has been called the myelin fraction water (MWF), which has been shown to correlate with tissue myelin fraction ³¹.

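### The study sets out to find the most sensitive and reliable MRI methods, but section 3.4 contains no analysis that compares methods

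*Combined protocol and SAP*

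**What the plan says.** Section 1.3 gives two purposes for the imaging. The primary outcome is whether tissue damage improves and then stabilises or repairs. The second purpose is methodological: the modalities are studied "to determine which of these are the most sensitive and reliable in detecting microstructural damage and repair over time", with the results "providing a guide for selecting the most appropriate MRI and immune methods to assess treatment efficacy in MS".

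The specific aims that follow take one modality at a time and ask whether it improves under treatment. I count eight modalities: conventional MRI, quantitative T1/T2, perfusion, Ktrans, OEF, mcDESPOT, MTI and DTI.

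Section 3.4 is the whole statistical plan:
- on the significance level, it says "All hypothesis testing will be at the 0.05 level of significance";
- on the model for repeated scans, it says "For longitudinal data, mixed effects regression model will be used to summarize patterns over the one-year period";
- on links from one measure to another, it says "Correlation analyses between specific measures will be accomplished using Pearson's correlation co-efficient";
- beyond that, it lists descriptive summaries by visit.

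On size, section 3.1a says "Sample size under consideration is 18 patients". On reliability, the only figure is in the MRI supplement under Quantitative Perfusion: "Test-retest reliability of cerebral perfusion has been measured to be better than 14" per cent. On coverage, the supplement gives Ktrans "four slices of 8-mm thickness" and perfusion fifteen slices of 3 mm, while mcDESPOT is whole-brain.

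**The concern.** A claim that one method is more sensitive than another needs a measure of sensitivity and a direct comparison of the two. Section 3.4 defines neither. A mixed model fitted to one modality shows whether that modality changed. A Pearson correlation shows whether two measures move together, not which responds more. Reliability needs repeat measurements under unchanged conditions, and the schedule has one scan per visit, at baseline and months 1, 3, 6 and 12.

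Without a stated rule, the obvious informal one is to see which modalities reach p<0.05. That rule is unsound, because a difference in significance is not a test of a difference in sensitivity. What is at stake is the promised guide for future MS trials. The within-modality question, which is the primary outcome, is not affected.

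**Working it through.** **What the plan offers against what the aim needs**

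| Needed for the aim | In section 3.4 or the supplement |
|---|---|
| A sensitivity measure common to all modalities | None |
| A between-modality contrast | None; correlations of unnamed pairs measure association |
| A reliability statistic and repeat scans | None; one earlier figure, for perfusion only |
| A rule for preferring one method | None |

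The plan states no power, effect size or SD, so there is no figure of its own to reproduce. What follows illustrates what would happen if significance were used as the rule.

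**Inputs.** From the documents: n = 18, level 0.05. Assumed: two-sided tests; one baseline-to-follow-up change per patient and modality; normal, complete data; true standardised change d equal in all modalities; equal correlation r between modalities.

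**Step 1, power for one modality.** For a paired t-test, the noncentral t with 17 degrees of freedom and noncentrality d√18 gives power p = 0.516 at d = 0.5, 0.799 at d = 0.7 and 0.979 at d = 1.0.

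**Step 2, two equally sensitive methods.** If independent, the chance that exactly one is significant is 2p(1−p):
- d = 0.5: 2 × 0.516 × 0.484 = 0.50
- d = 0.7: 2 × 0.799 × 0.201 = 0.32

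At r = 0.5, simulation (20,000 to 40,000 trials) gives about 35% and 24%; repeat runs vary by about a percentage point.

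**Step 3, eight equally sensitive methods.** If independent, the chance that some are significant and others not is 1 − p⁸ − (1−p)⁸:
- d = 0.5: 1 − 0.005 − 0.003 = 0.992
- d = 0.7: 1 − 0.166 − 0.000 = 0.834
- d = 1.0: 1 − 0.844 − 0.000 = 0.156

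With correlation, by simulation:

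| True change d | r = 0 | r = 0.5 | r = 0.7 |
|---|---|---|---|
| 0.5 | 99% | 80% | 64% |
| 0.7 | 83% | 58–59% | 45% |
| 1.0 | 16% | 11% | 9% |

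**Step 4, what a direct comparison could show.** The standardised response mean (SRM) is the mean change divided by the SD of change. For two equal methods at r = 0.5 and n = 18, the simulated SD of the difference in SRM is 0.28 at d = 0.5 and just over 0.30 at d = 0.7. The 95% half-widths are 1.96 × 0.28 = 0.55 and about 0.60. For true values of 0.8 against 0.5, approximate power to detect the difference is 17% at r = 0.5 and 12% at r = 0.

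**Step 5, coverage.** If slices are contiguous, Ktrans spans 4 × 8 = 32 mm and perfusion 15 × 3 = 45 mm, against the whole brain for mcDESPOT. The eligibility criteria ask only for an enhancing CNS lesion, so a lesion may fall outside a slab.

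**The case against.** A reader might infer that the trial will rank modalities by p-value. The documents do not say so: section 3.4 speaks of summarising patterns and also lists correlations and descriptive statistics. One test per modality is a natural reading of the separate aims together with the 0.05 sentence, not a stated rule. What stands is narrower: the plan does not say how methods will be compared.

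A reader might also take the 99% to 83% figures as the size of the problem. They need independence, which is doubtful for scans of the same patients; section 1.3 itself describes MTI as complementing MWF. With correlation the figures fall, and with large effects they become small.

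Nor do the documents show that the methods see different lesions. Slab placement is not given, and the perfusion and Ktrans aims are directed at active lesions. Different sampling is possible, not established.

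It is also fair to say that method selection is not the primary outcome, that no specific aim ranks methods, and that 18 patients would seldom settle a ranking. This argues for a descriptive label. It does not supply the missing comparison, because the purpose and its intended use are stated plainly in section 1.3.

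**Conclusion.** The point holds as a gap between a stated purpose and the planned analysis: nothing in section 3.4 can show which modality is more sensitive, and nothing in the schedule can establish which is more reliable. This conclusion rests on the text and needs no assumed effect size.

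The chance-split figures are conditional. They apply only if significance were used to choose methods, and they depend on an assumed true change and correlation that the documents do not give. Over changes of 0.5 to 1.0 SD and correlations of 0 to 0.7, the eight-method figure runs from 99% down to 9%. The limited slabs are a possible further source of non-comparability.

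The plan should be changed, but the defect does not undermine the within-modality results.

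**What to change.** Add to section 3.4:

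- For each modality, with one metric and its direction of improvement named in advance, the SRM from baseline to months 1, 3, 6 and 12. Use the same patients and the lesions covered by the methods being compared, and report how many patients and lesions remain.
- Pairwise differences in SRM with intervals from a bootstrap that resamples patients, not lesions. Declare no ranking where the interval includes zero.
- Separate interpretation of the Gd+ and Ktrans measures from the microstructural measures (MWF, MTR, DTI, quantitative T1). Lesions enter the study because they enhance, and section 1.3 says enhancement lasts under two months on average. A large response on Gd+ or Ktrans therefore partly reflects that selection.
- A statement that the comparison is descriptive.

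Delete reliability from the aim in section 1.3. Using visit-to-visit variation in normal-appearing white matter instead would not rescue it: the supplement uses that tissue as an internal reference for quantitative T1, so that method could look falsely stable. Variation between months 6 and 12 would also mix measurement error with true change, as section 3.3 allows a switch of disease-modifying therapy after month 1.

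The cost is extra analysis of scans already planned. Restricting to common lesions may leave fewer than 18 patients, and section 3.5 plans no replacement of patients who withdraw after treatment. Even at 18, half-widths of about 0.55 to 0.60 (at correlation 0.5) mean the comparison will often be inconclusive.

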Specific aim: Compare OEF in MS patients undergoing a relapse before and after ACTHAR treatment and observe any improvement in OEF indices post-relapse treatment.

Multi-component driven equilibrium single pulse obervation of T1/T2 (mcDESPOT): This is a fairly new technique to assess the water content of myelin. In an active MS lesion, the overall water content of the lesion increases, but the water associated with myelin decreases, implying loss of integrity of myelin. Hence, a decrease in MWF is a marker of myelin damage ^{12, 13}. MS lesions are associated with a low MWF initially which improves over time as the lesion repairs.

Specific aim: Determine whether ACTHAR treatment is associated with an improvement in MWF of active (Gd+) and inactive T2 lesions over time.

Magnetization transfer imaging (MTI): this imaging modality complements MWF in identifying changes in the microstructure of both white matter and gray matter. MTI improves over time as lesions heal/remyelinate ^{14, 15, 16}. This technique will be used to assess lesion resolution/repair over time.

Specific Aim: Determine whether ACTHAR treatment is associated with an improvement in MTR of active (Gd+) and inactive T2 lesions over time

Diffusion Tensor Imaging (DTI): This is a technique has an advantage over the MWF imaging and MTR in that it can interrogate both myelin ($\lambda \perp$) and axonal loss (λ II) based on transverse and axial diffusivities. There is evidence that alteration in DTI parameters in acute MS lesions have predictive value in terms of long term T1 black hole evolution ¹⁷.

Specific aim: Determine whether ACTHAR treatment is associated with an improvement in DTI metrics of active (Gd+) and inactive T2 lesions over time.

Part II. Corresponding immune studies:

2.1 Overview and Rationale

Purpose and Rationale

MS is immune-mediated. The process involves deregulated immune response of T and B lymphocytes, and macrophages. Autoreactive T cells expand, creating a shift in the balance of pro- and anti-inflammatory cytokines that favors inflammation. The antigen triggering MS is unknown.

ACTH therapy produces rapid and robust recoveries during exacerbations ¹⁸⁻²⁰. ACTH induces anti-inflammatory and immunomodulatory functions involving T and B lymphocytes and macrophages; it activates the sympathetic nervous system to reduce inflammation; it reduces pro-inflammatory cytokines through inhibition of NF- κ B signaling, and inhibits expression of nitric oxide and adhesion molecules; and it enhances production of anti-inflammatory IL-10 ^{6, 21}.

In MS, there are defects In CD4 and CD8 regulatory cell function. Tregs normally reduce and control the intensity of an immune response ²². Accumulating evidence indicates an immunosuppressive role for CD4+CD25+Tregs in immune-mediated diseases. Venken and colleagues suggested that the suppressive capacity of these CD4+CD25+Tregs appears to be more affected in the early phases of MS ²³, but Antel et al. found that CD8 Tregs were more affected in the progressive phase ²⁴.

There are differences in function that correlate with expression of FOXP3, a master regulator in the development and function of regulatory CD4+CD25+T cells), which are adequate in patients with SPMS but reduced in those with RRMS ²³. More recently, Correale and Villa investigated the role of CD8+CD25+FOXP3 cells in RRMS patients, as the role of CD8+ has received less recent attention than CD4+ cells ²². CD8+CD25+FOXP3 cells are suppressed to a greater degree in the peripheral blood during MS exacerbations than during remission or in healthy controls. Likewise, in the cerebrospinal fluid (CSF) of MS patients during exacerbations, lower levels of CD8+CD25+FOXP3 T cells are detected, providing evidence for a previously unknown CNS mechanism involved in immune regulation in MS ²².

We and others find the regulatory deficit is largely constrained to the CD8 population ^{22,}

^{25, 26}. CD8 regulatory/suppressor cell function is slightly reduced in stable MS, very low during attacks and progression, and rebounds during recovery ²⁵. The defect is localized to the CD8+CD28- population ^{22, 27, 28}, a better marker than FOXP3 in this subpopulation ²⁶. We have found that CD8+CD28-Treg cells are very low in therapy-naive MS compared to healthy controls. Some MS immune modulators can elevate numbers of this subpopulation, and thus enhance anti-inflammatory functions and reduce inflammatory Th1/Th17 functions (Figure 1 below) ²⁹.

Figure 1. CD8 regulatory cell expression (CD8+CD28- T cells, arrows) is subnormal in MS (second panel) compared to healthy controls (first panel), however this low expression can be up-regulated with immune modulator (third panel).

We also illustrate our capabilities for measuring gene expression (Figure 2) and serum

yet still had markedly suppressed RNA expression for 5,000 differentially-expressed genes compared to therapy-naïve exacerbations in right panel. x-axis = fold down (to L) or up (to R); y-axis = significance

Figure 3. Multiplex analysis of proteins expressed by activated MNC. Cells were exposed to media only or to an agent that affects MS exacerbations and progression, then activated for 48 hours. Supernatants were analyzed for Th1, Th17, Th2, IFN-stimulated genes, and adhesion molecules (shown here), in addition to monokines, B cell factors, and neuroprotective proteins (dns). Columns are different patient and control groups, row are heat maps of average expression. Red = increased expression vs. media control; Blue = decreased expression vs. control; hue = statistical significance, with more saturation having lower p values (more zeros).

2.2 The hypothesis is that ACTHAR treatment in MS relapses generates a tolerogenic immune environment that suppresses inflammation and facilitates brain repair. We've found that CD8+CD28- suppressor cells are low in MS and are upregulated by several classes of immune modulators. The tolerogenic immune environment will be assessed in 18 ACTHAR-treated MS patients.

2.3 Overall objective is to determine Treg expression and neuroprotection signature, as well as identify gene and immune protein signatures in ACTH-treated MS:

2.4 Specific aims and experiment design with serum, MNC, and RNA samples from baseline, last day of ACTHAR (day 10 of therapy), 1 month post 1st dose, and months 3 and 6:

- 1. **Aim1**. Determine immune subset expression in CD4+FOXP3 Tregs and CD8+CD28- T suppressor cells by flow cytometry at each visit above.
- 2. **Aim 2**. Determine global gene expression profiling in MNC with 913,000 probes at each visit above. Bioinformatics will include pathway analysis and ACTHAR-induced RNA signature.
- 3. **Aim 3**. Determine serum protein profiling for immune-regulated cytokines (Th1, Th2, Th17, monokines...) and neuroprotective proteins (NGF, BDNF, ACTH, HGF, CNTF, IL-10...) at each visit above.

4. **Aim 4.** All data from protein and gene expression, as well as immune subset expression will be compared to our database generated from therapy-naïve stable and exacerbating MS. ACTHAR signature will analyzed based on these comparisons.

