Effects of ACTHAR on Advanced MRI Surrogate Markers of Disease Activity and on Comprehensive Immune Signature During MS Relapses IRB16-1390 NCT3021317 Protocol Date 10/23/19

Effects of ACTHAR on advanced MRI surrogate markers of disease activity and on comprehensive immune signature during MS relapses

This investigator-initiated trial (IST) is divided into two complementary parts:

- Advanced serial MRI studies on patients during and after an acute MS relapse. MRI will be performed at baseline, 1 month after the 1st dose of ACTHAR, and months 3, 6, and 12. ACTHAR will be administered for 10 days. Patients will start ACTHAR within 48 hours of relapse assessment.
- Serial immune assays on patients during and after an acute MS relapse. Serum and blood samples with be collected at baseline, last day of ACTHAR (day 10 of therapy), 1 month post 1st dose, and months 3 and 6.

ACTHAR will be administered by a self-injectable syringe under the skin fat tissue (subcutaneous injection). The first subcutaneous injection of ACTHAR will be done in the clinic. Subjects will undergo a teaching session with the PI ([name]) about how to give a subcutaneous injection of ACTHAR. All subsequent injections will be self-administered by the patient.

At each research visit, subjects will have a physical/neurological examination, blood pressure, height, weight, and temperature taken at the time of visits. Urine pregnancy test or urine analysis may be done if there is a clinical concern for pregnancy or urine infection. This will be based on the discretion of the investigators.

Part I. Investigational Plan-MRI

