1.1 Overview

Multiple sclerosis (MS) is a demyelinating disease of the CNS. In a vast majority of patients, its clinical course is characterized by transient attacks of acute neurological compromise, followed by variable degree of recovery. Each relapse leaves a patient with some degree of residual disability. Higher number and longer duration of relapses are associated with greater loss of function. Hence, it is imperative that these relapses are optimally treated and curtailed in duration to allow for maximal recovery and repair.

ACTH (ACTHAR or IV formulation) has long been used for the treatment of MS relapses ^{1, 2}. ACTH has equivalent efficacy to high-dose IV methyprednisolone in curtailing the duration of MS relapses ^{3, 4}. ACTH has an advantage over steroids in that it has a short half-life and much less deleterious steroidogenic effect on bone and fat metabolism ⁵. Importantly, ACTH has a unique mechanism of action on immune and brain cells through melanocortin receptors (MCRs), which promote production of regulatory and anti-inflammatory cytokines and support oligodendrocyte precursors and neuronal function, all of which could lead to better repair of MS lesions and favorable clinical outcome ⁶.

Several studies have shown beneficial effects of ACTHAR on clinical relapses ⁷. However, there is little *if any* knowledge about the benefits of ACTHAR in suppressing inflammatory lesion activity and enhancing remyelination over time as assessed by MRI. Improvement in the inflammatory activity, and particularly repair, in MS lesions leads to

improved clinical outcome and less residual clinical deficit. Often during the MS course, the ratio of new MRI disease activity to clinical relapses can be 10:1. Hence, suppression of this MRI activity is relavant to clinical outcome.

The studies proposed herein will provide a better understanding of the effects of ACTHAR in improving MRI lesion characteristics over time. The complementary immune and genetic studies will further provide evidence for the mechanism of action (MOA) of ACTHAR in improving immune dysfunction related to MS relapse. This is a one of a kind study, involving both advanced/state-of-the art MRI techniques and immune studies to assess the beneficial effects of ACTHAR in MS relapses in the same patients over time.

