2.5 Methods

Blood is drawn from 18 MS patients at baseline, last day of ACTHAR (day 10 of therapy), 1 month post 1st dose, and months 3 and 6. Mononuclear cells (MNCs) from four 8cc heparin green-top tubes (40-60 million cells) are separated on Ficoll-Paque gradients. 30M cells are needed for flow cytometry. 20M cells are needed for total RNA preparation.

Specific Aim 1. Determination of ACTHAR effects on immune cell subsets in relapsing remitting MS (RRMS), emphasizing expression on CD8 cells including the CD8+CD28-regulatory subset. Flow cytometry will be conducted to determine the effect of ACTHAR on in vivo expression of surface markers on T cells (CD4, CD8, CD28, FOXP3). Reagents are from e-Biosciences and B-D. (MAbs = CD4, CD8, CD28, CD27, CD25, FOXP3).

Specific Aim 2. Global gene expression profiling in MNC will be measured with 913,000 probes at each sample. Bioinformatics will include pathway analysis and ACTHAR-induced RNA signature. Total RNA will be isolated from 20M cells, as the template for synthesizing cDNA for gene expression array analysis with Affy HTA kit. RT-PCR will be performed for validation of specific gene signatures.

Specific Aim 3. Serum from each sample will be applied on Procarta multiplex assay plates according to manufacturer's instruction. Immune, neuroprotection, and other proteins will be measured with 40 highly-selected targeted antibodies for Th1, Th2, Th17, monocyte, neuroprotection, cell proliferation and death, and adhesion molecule panels.

Specific Aim 4. Advanced bioinformatics with Gene Set Variation Analysis:

- 1. Identify differential gene expression (DEG) between groups;
- 2. Analyze pathways by Ingenuity Pathway Analysis (IPA);
- 3. Discover transcriptional signature of genes and gene pathways;

4. Build a predictive model using machine learning algorithms including Random Forests (RFs) and Support Vector Machines (SVMs).

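### Serum ACTH is listed as a neuroprotective outcome protein although ACTH is the study drug; its day-10 value cannot be read as a response to treatment

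*Combined protocol and SAP*

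**What the plan says.** - **The outcome.** Section 2.4, Aim 3 names the serum proteins to be profiled, among them "neuroprotective proteins (NGF, BDNF, ACTH, HGF, CNTF, IL-10...) at each visit above". ACTH is one of six proteins named in an open-ended list.
- **The drug.** Section 1.1 treats ACTHAR as a form of ACTH: "ACTH (ACTHAR or IV formulation) has long been used for the treatment of MS relapses". The opening summary states that "ACTHAR will be administered for 10 days".
- **The sampling times.** After baseline, section 2.5 schedules blood on the "last day of ACTHAR (day 10 of therapy), 1 month post 1st dose, and months 3 and 6". Section 2.4 gives the same times.
- **The use.** The objective in section 2.3 is to "determine Treg expression and neuroprotection signature, as well as identify gene and immune protein signatures in ACTH-treated MS". Aim 4 in section 2.4 compares all protein, gene and cell-subset data with the group's database of therapy-naïve stable and relapsing patients, and derives the ACTHAR signature from those comparisons. Section 2.6 adds that serum proteins might serve as markers of efficacy.
- **Timing of doses.** Section 1.1 says "ACTH has an advantage over steroids in that it has a short half-life". After the first clinic dose, "All subsequent injections will be self-administered by the patient". Section 3.2 allows a second 10-day course for an inadequate response after 14 days.

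The documents do not separate injected from endogenous ACTH or label serum ACTH as an exposure measure. They do not exclude it from any signature, and they do not fix the day-10 draw relative to the last injection.

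**The concern.** A response measure should be able to come out either way under the treatment being tested. IL-10, in the same list, meets that test: section 2.1 describes it as something ACTH increases. ACTH itself is the input. If both are counted in one outcome class, the intervention can be credited as part of its own effect.

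What is at stake is the interpretation of two results: the neuroprotection signature at day 10, and the comparison of treated patients with a database of patients who were not given ACTH. On this analyte, a difference could appear in either even if ACTHAR had no immune or neuroprotective effect.

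**Working it through.** The plan gives no figure on this point, so there is none to reproduce. The check is a reading of the sections together, followed by one illustration on assumed inputs.

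**1. What a day-10 value can mean.** The documents do not say whether the multiplex antibody detects the injected product.
- If it does, the value contains drug, and depends on the time since the last injection. With a half-life described as short and home injection at no specified hour, that interval can differ between patients.
- If it detects only the patient's own hormone, the value shows how the pituitary responds to dosing.

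Neither reading gives a neuroprotective response that is independent of the injection.

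**2. Which samples are affected.** Take one month as about 30 days.
- Day 10: on drug by design, 1 of the 4 post-baseline samples.
- Month 1: about 20 days after a single course (30 − 10). With a second course, the answer depends on how the 14 days in section 3.2 are counted. From the first dose, the course could end at about day 14 + 10 = 24. From the end of the first course, it could end at about day 10 + 14 + 10 = 34, which would span the month-1 draw. Section 3.2 does not say which is meant, nor how soon a second course starts.
- Months 3 and 6: well after either course, so direct exposure should be negligible given the short half-life.

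**3. Where the value goes.** Aim 4 in section 2.4 covers all protein data and makes no exception for ACTH. The comparison patients are therapy-naïve, so injection status and group coincide, and a day-10 difference in ACTH cannot be attributed to anything else.

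**4. How large it could be (illustration only).** No formula for the signature exists, so one is assumed: the equal-weight mean of m standardised changes with common correlation ρ. Only ACTH shifts, by k SD of change. The test is a two-sided one-sample t test with n = 18 (section 3.1a) and α = 0.05 (section 3.4; two-sidedness is assumed).

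Standardised shift of the score: d = (k/m) / √[(1 + (m − 1)ρ)/m]. Noncentrality: d√18, on 17 degrees of freedom.

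Example: m = 6, ρ = 0, k = 1 gives d = (1/6)/√(1/6) = 0.408, and the probability of a significant score is 0.373.

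| m | ρ | k = 1 | k = 2 | k = 3 |
|---|---|---|---|---|
| 6 | 0 | 0.373 | 0.904 | 0.998 |
| 6 | 0.3 | 0.179 | 0.542 | 0.872 |
| 40 | 0 | 0.097 | 0.245 | 0.476 |
| 40 | 0.3 | 0.054 | 0.065 | 0.083 |

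With ACTH left out and no other protein changing, every cell is 0.05. Here m = 6 is the number of neuroprotective proteins named in Aim 3, and m = 40 is the number of antibodies in section 2.5. The values of k and ρ and the equal weights are assumptions.

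**The case against.** Listing ACTH as neuroprotective follows the protocol's own rationale: section 1.1 says it acts through melanocortin receptors on immune and brain cells and supports oligodendrocyte precursors and neurons. Aim 3 speaks of profiling, not of proof of effect. If analytes are reported one at a time, a reader will recognise ACTH as the drug and nothing else is contaminated. This explains why the hormone is measured. It does not make its level during dosing a response, and sections 2.3 and 2.4 do plan signatures rather than only a list.

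The objection is right about several stronger readings that a reader might infer:
- *A day-10 rise is close to guaranteed.* Not supported: it depends on an unstated assay property and on the time since injection. With a short half-life, the value could be near baseline.
- *The predictive model is contaminated.* Not established: in section 2.5 the model comes at the end of a gene-expression pipeline. No serum protein is named as an input and no prediction target is stated.
- *Injection and draw times are unrecorded.* The protocol does not specify them; the case report forms are not part of these documents.
- *ACTH is one of the 40 assay targets.* This is an inference, because the 40 antibodies are not itemised.
- *The database comparison will show a difference in ACTH.* The documents do not say that the database holds serum ACTH.

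**Conclusion.** The point stands in limited form. Serum ACTH at day 10, and possibly at month 1 after a second course, cannot count as an independent neuroprotective outcome. On this analyte, a difference between treated patients and the therapy-naïve database cannot be separated from injection.

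The size is unknown. In the assumed scores, the chance of a significant result due to ACTH alone runs from about 5% (essentially nominal) to 99.8%. That spread shows only that the answer depends on a signature definition the plan does not give. It is not an estimate for this trial.

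It would be wrong to infer that the whole signature measures drug exposure. The other named proteins are not the drug, months 3 and 6 should be largely unaffected, and the MRI outcomes do not use this value. Severity is minor, confined to the mechanistic immune aims. The classification of ACTH is explicit in the text; entry into a signature follows from Aims 3 and 4 and not from a stated formula.

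**What to change.** - In Aim 3, move ACTH out of the neuroprotective proteins. Keep measuring it at every visit, and report it separately as an exposure measure.
- State that it is excluded from the neuroprotection signature and from the protein-based ACTHAR signature in Aim 4. Exclude it from the predictive model too, if serum proteins are used as inputs.
- Record the date and time of the last injection and of the day-10 draw, so that the value can be interpreted. When reading month-1 ACTH values, identify patients who had a second course.

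The cost is a few lines of wording, two recorded times and one fewer analyte in the signature. Samples and assay stay the same.
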